## What to do if complete inhibition is not achieved during the Initiation Phase?

Failure to respond adequately during this phase may prompt the Investigator to consider withdrawing the patient from the study (clinical symptoms will be taken into account) and switching him/her to alternative complement inhibitory therapy if available.

#### Maintenance Phase Day 29-180 (±3 day window)

At Day 29 the patient will attend clinic. All procedures and blood draws will be performed predose as per the schedule of events (Table 11). The patient will then administer their 45 mg once a day dose in clinic.

## Intensive Monitoring Clinic Day 36-37 (±3 day window)

If the patient is responding well to once daily dosing, an overnight stay is required at Day 36 to perform Intensive PK sampling at timepoints 3hrs, 6hrs, 9hrs, 12hrs, 18hrs & 24hrs. A 30-minute window to draw blood is permitted.

On Day 43 a clinic visit will take place and a local and central blood draw will be taken.

Central and local Blood draws will be taken at the clinic during the clinic visits on Day 60, 90, 120, 150 and 180 (±3 day window).

## How to Manage a Hemolytic Episode?

If there is any indication that the patient is experiencing a hemolytic episode, the patient is instructed to contact the site using the emergency numbers provided.

## **Unscheduled Visits**

All patients will return to the hospital clinic to meet with the Investigator at intervals shown on the schedule of events (Table 11). More frequent visits may be necessary at the discretion of the Investigator.

## Additional Blood Draws

If the patient experiences an AE, the Investigator will determine whether a safety blood draw is required. If the safety blood draw includes a CH50 analysis that sample will be sent to the central laboratory.

## Follow Up Visit – Day 210 (+5 days)

At Day 210 (+5 days), a follow up visit will occur to ensure all outstanding or new AEs are addressed. Patients entering the long-term safety trial are excluded from the follow up visit.

## Entering the Long-Term Safety Trial

After 180 days, the patient may enter the long-term safety trial or begin an alternative treatment.

The decision to continue on Coversin after the 180 day treatment period should be made by the patient in consultation with the Investigator at or about the 150 day time point. This allows alternative treatment logistics to be arranged if the patient prefers alternative therapy after study completion.

If the patient and Investigator are satisfied with Coversin treatment the patient may enroll onto the long-term safety trial at Day 181. Coversin will be provided through this mechanism until it is approved and locally reimbursed.

## **5.3 Procedure for Increase in Frequency of Doses**

Evidence from animal PK/PD studies, single and multiple dose studies in normal volunteers and experience in 10 patients suggest that an inadequate response or breakthrough hemolysis is highly unlikely to occur during the AD or Initiation Phase.

On completion of the Initiation Phase, a single 45 mg daily maintenance dose will be given for the remainder of the trial unless, it becomes apparent that full complement inhibition is not being maintained, in which case appropriate dose interval adjustments will be made and the patient will revert back to 22.5 mg twice daily after receiving another AD.

The maintenance dose can be changed after Day 36 if there is evidence of CH50 > 10 CH50 U Eq/mL, a rise in serum LDH for two consecutive readings of over 0.4 x ULN or a single rise over 0.8 x ULN above the lowest level previously achieved or clinical symptoms. In this case the dose should revert back to 12-hourly dosing (assuming compliance is satisfactory and that the patient has not missed any doses) or consideration should be given to the patient withdrawing from the study.

The schedule for dosing during the Initiation and Maintenance Phases, is as follows:

	Inadequate	Response		
Exis	ting	Swit	tch to	
Dose	Interval	Dose	Interval	
22.5 mg	12 hourly	Withdraw patient		
45 mg	24 hourly	22.5 mg	12 hourly	

## Table 10Schedule of Dosing for Initiation & Maintenance Phase

In patients with exceptionally low body fat (<16%) it may be difficult for a reservoir effect to be set up, resulting in over-rapid absorption of the dose into the blood stream and loss of any excess Coversin via the kidneys. These patients may benefit from divided dosing (12 hourly) and it is suggested that consideration should be given to dividing the dose into two 12 hourly increments in patients with low body fat who are not responding optimally to 45 mg/day given as a single dose.

Samples for CH50, antibodies and drug level should be processed as shown in the Laboratory Manual and sent to a central laboratory. All other laboratory tests should be done locally in the PI's hospital laboratory. Extra samples for PK/PD may be taken at the discretion of the Investigators during illness or infection.

The patient will continue treatment for 6 months or until it has been decided by the Investigator in consultation with the Sponsor that further Coversin treatment is futile or not in the patient's best interests.

If Coversin therapy is discontinued for any reason, all patients will be followed for a minimum of 30 days. Any patient with an unresolved adverse event at that time will be followed until resolution or until stabilization and when no further improvement is anticipated.

# 5.4 Missed Doses

A missed dose is defined as a dose not taken within greater than a two-hour time window after the earliest time the patient would normally dose. For example, a patient may normally dose with drug at 8am, but the patient is permitted to dose between 7am and 9am (i.e. +/- 1 hour of usual 8am dosing time) without this being considered a missed dose.

## Patient on a twice daily dose of 22.5 mg

a) The patient becomes aware of a missed dose more than 2 hours but less than 6 hours after the earliest time they would normally administer a 22.5 mg dose. The patient should immediately contact a research nurse for advice then shortly afterwards take their current 22.5 mg dose and then resume their usual 22.5 mg twice daily dosing schedule. For example, a patient who normally takes their evening 22.5 mg dose at 8pm realizes at 10pm that they forgot to take their dose at the usual time. The patient should dose themselves with 22.5 mg of drug then resume 22.5 mg twice daily dosing at the usual time of their morning dose the next day.

- b) The patient becomes aware of a missed dose 6 -12 hours after the earliest time they would normally administer a 22.5 mg dose. The patient should immediately contact a research nurse for advice then shortly afterwards take a 45 mg dose and then resume their usual 22.5 mg twice daily dosing schedule. For example, a patient who normally takes their evening 22.5 mg dose at 8pm each evening realizes at 7am the next day that they forgot to take their dose the night before. The patient should dose themselves with 45 mg of drug then resume 22.5 mg dosing at the usual time that evening.

#### Patient on a single daily dose of 45 mg

- a) Patient becomes aware of a missed dose more than 2 hours but less than 16 hours after the earliest time they would normally administer a 45 mg dose. The patient should immediately contact a research nurse for advice and then shortly afterwards take a dose of their current dosing schedule (45 mg) and then resume the usual dosing schedule at the specified time. For example, a patient who normally doses themselves at 8am each morning realizes at 10am that they forgot to take their dose at the usual time. The patient should speak to a research nurse for advice and then dose themselves with 45 mg of drug then resume 45 mg dosing at 8am the next day.
- b) Patient becomes aware of a missed dose 16 to 24 hours after the earliest time they would normally administer a 45 mg dose. The patient should immediately contact a research nurse for advice and then shortly afterwards administer an ablating dose of 60 mg followed by a 30 mg dose 12 hours later and then resume their usual 45 mg dosing schedule the next day. If the research nurse cannot be contacted within 60 minutes the patient should not delay further but go ahead and administer the ablating dose of 60 mg followed by a 30 mg dose 12 hours later. For example, a patient who normally doses themselves at 8am each morning, realizes at 7am the next day that they forgot to take their once daily 45 mg dose the previous

Page 54 of 84 AKARI Confidential day. The patient should dose themselves with 60 mg followed by 30 mg 12h later then resume their 45 mg once daily dose at 8am the next day.

- c) Patient becomes aware that they have missed two or more doses. The patient should immediately contact a research nurse for advice and then shortly afterwards administer an ablating dose of 60 mg followed by a 30 mg dose 12 hours later and then resume their usual 45 mg dosing schedule the next day. If the research nurse cannot be contacted within 60 minutes the patient should not delay further but go ahead and administer the ablating dose of 60 mg followed by a 30 mg dose 12 hours. The patient should then resume their usual dosing schedule of 45 mg each morning. For example, a patient realizes they have forgotten to take their once daily 45 mg dose for two days. The patient should dose themselves with 60 mg followed by 30 mg 12h later then resume their 45 mg once daily dose at 8am the next day. The patient should arrange to see their clinician within the next few days.
- d) Patient misses two or more doses. The patient should take an immediate ablating dose of 60 mg followed by a 30 mg dose 12 hours later and then resume the usual dosing schedule at their specified times. The patient should inform the research nurse as soon as possible.

# The missed dose guidelines are intended to ensure that patients do not inject more than 90 mg in a 24-hour period.

The clinic staff should support the patient to prepare the 60 mg and 30 mg dose over the phone or via a clinic visit.

In all cases the clinic staff may arrange for a blood draw to be taken at 24 hourly intervals after first becoming aware of missed doses to ensure the situation is under control. The sample for PD (CH50) analysis should be taken just prior to the next morning dose of Coversin. As the CH50 results are unlikely to be available for some days the Investigator should be guided by the disease history, clinical signs and measures, including platelet count and LDH to determine next steps.

If 3 or more consecutive doses have been missed the patient's ability or willingness to comply with the protocol should be discussed and consideration should be given as to whether that patient should continue in the study.

## **6** STOPPING RULES AND DISCONTINUATION CRITERIA

## 6.1 Definition of Inadequate Response

An inadequate response to Coversin treatment is defined as any of the following events:

- A persistent rise in CH50 to >10 U Eq/mL at any time after Day 2
- A rise in serum LDH for two consecutive readings of over 0.4 x ULN or a single rise over 0.8 x ULN above the lowest previously achieved. A LDH measurement (unscheduled visit) should be made a couple of days after the first LDH reading of 0.8 x ULN to confirm the result before deciding whether or not to switch the patient to 22.5 mg q.12h.
- Persistent clinical symptoms considered by the clinical investigator to indicate that control of the disease is worsening

The decision to revert a patient from 45 mg QD dosing back to 22.5 mg q.12 h dosing should be made on the following basis by means of consultation between site clinical investigator and the Sponsor's Medical Director:

- In consultation with the patient, consideration should be given as to whether patient compliance with drug administration (dose, dose technique, dose frequency and dose interval) is satisfactory. Particular consideration should be given as to whether or not a patient has missed one or more recent doses.
- If compliance is considered satisfactory the patient may benefit from a switch to 22.5 mg q.12h dosing and consideration of other factors (described below) should be used to determine whether the patient should switch to 22.5 mg q.12h dosing.
- If compliance is not considered satisfactory the patient should be retrained and re-ablated (60 mg followed by 30 mg 12 hours later) then continue on 45 mg QD dosing. 1-2 weeks after retraining the patient should be brought into the clinic for assessment of CH50, LDH and symptoms. If no improvement is seen the patient should be switched to 22.5 mg q.12h.
- Consideration should be given as to whether or not the rise in CH50, LDH or worsening symptoms may be explained by an ongoing infection or newly arisen comorbidity or a worsening comorbidity.
- If the infection or comorbidity is likely to be acute consider maintaining the 45 mg QD dose until the infection or comorbidity has resolved. Patient should be monitored via unscheduled visits if need be. If CH50, LDH or worsening symptoms do not improve after the infection or comorbidity has resolved patient should be switched to 22.5 mg q.12 h.
- If the infection or comorbidity is likely to be chronic plan a second clinical visit a few days later to assess whether CH50, LDH and symptoms are still elevated before then switching to 22.5 mg q.12h.

All patients reverting to q.12 h. dosing will receive another AD first (60 mg followed by 30 mg 12 hours later). An overnight stay is not required but patients should be trained by hospital staff on how to prepare the 60 mg and 30 mg dose. The patients will also have the instructions in the dosing instructions manual.

Patients who are considered to still have an inadequate clinical response 3 weeks after dividing the 45 mg QD dose to 22.5 mg q.12 h. will be deemed treatment failures and withdrawn from the study. Any patient being withdrawn will have all last visit assessments performed at that time.

Patients who are moved to q.12 h. dosing as a result of a rise in LDH associated with a possible stress event such as long-term infection or comorbidity that eventually resolves may, at the discretion of the PI, and in consultation with the Sponsor's Medical Director, go back onto once a day 45 mg dosing. This change back to 45 mg QD should not take place less than 30 days from the start of the q.12 h. dosing and should only occur if CH50, LDH and symptoms have fallen back to acceptable levels.

## 6.2 Events Triggering Consideration of Alteration of the Dose or Dose Interval

In order that patients receive optimal complement inhibition and disease control, it is important that patients who may benefit from a change to 12 hourly dosing, rather than once daily, are identified as early as possible. In all cases a careful assessment of compliance and injection technique should be made with the patient. Assuming adequate drug administration is confirmed, the following event mandates administering an AD and reverting to 12 hourly dosing immediately:

• Clinical evidence of a thrombotic event after Day 29

One or more of the events listed below should prompt suspicion of inadequate control and consideration of reverting to 12 hourly dosing (if in the MP) or withdrawing the patient. In all cases the clinician should take into account the overall clinical status of the patient, whether there is a continuing trend towards improving disease control and whether extrinsic factors (e.g. intercurrent infection) may have precipitated the event. Before deciding to revert to 12 hourly dosing or withdraw the patient, the Investigator should discuss the case with the Clinical Research Organization's (CRO) and the Sponsor's Medical Director. These events are:

- Clinical evidence of intravascular hemolysis (macroscopic hemoglobinuria)
- Whilst no absolute value can be set for this, successful control of PNH should result in a rapid and sustained fall in LDH between Day 1 and Day 28 of treatment. Typically, the fall will be to 50% or less of pre-treatment levels by Day 7 and a maximal reduction is normally seen by Day 28. However, Investigators should be guided by whether the LDH is continuing to fall between Day 1 and Day 28, rather than by absolute values. A rise in LDH of 0.8xULN above the lowest level previously achieved, or two consecutive rises of ≥ 0.4x ULN should be taken as mandating a reversion back to twice a day dosing, assuming that compliance is satisfactory and that the patient has not missed any doses.
- Unexplained rise in LDH for two or more consecutive readings at any time by >40% above the lowest value recorded after commencement of Coversin treatment
- CH50 >10 CH50 U Eq/mL on or after Day 14 providing that the assay has been performed by the Central laboratory

If after changing dosing regimen the patient is still inadequately controlled on the basis of the CH50 result (i.e. CH50 > 10 U Eq/mL), the Investigator should discuss with the Sponsor's Medical Director the possible withdrawal of the patient.

## 6.3 Withdrawal Criteria

In accordance with applicable regulations, a patient has the right to withdraw from the study at any time and for any reason without prejudice to their future medical care by the physician or at the Institution. Should a patient withdraw from the study, then the patient will not undergo any further study-specific procedures or receive any treatment mandated by the Protocol. All patients will be followed up for 30 days for safety.

If a patient fails to attend scheduled trial assessments, the Investigator must determine the reasons and the circumstances as completely and accurately as possible.

In the event of the premature withdrawal of a patient from the trial, the end of trial visit should be carried out as completely as possible. Minimally, a safety assessment should be performed.

Page 57 of 84 AKARI Confidential In the case of withdrawal due to the occurrence of unacceptable toxicity, the patient will be requested to remain under the supervision of the Investigator until the toxicity has resolved or is no longer considered to be clinically significant by the Investigator.

If an AE, classified as severe, results in patient withdrawal from the study, the patient will be followed until the AE (or SAE) resolves or stabilizes, and any interventions required to resolve or stabilize the event will be recorded in the electronic case report form (eCRF).

All withdrawals must be documented in the eCRF. A patient may be withdrawn in any of the following circumstances.

- Withdrawal of consent (mandatory withdrawal)
- Intake of non-permitted concomitant medication (may be discussed with the Sponsor and dependent on the nature of the medication)
- Patient is non-compliant with study procedures in the opinion of the Investigator (mandatory withdrawal)
- If discontinuation is considered necessary by the Investigator and/or Sponsor (mandatory withdrawal)
- Request of Regulatory Agency (mandatory withdrawal)
- Patient develops an illness that would compromise his participation in the study (may be discussed with Sponsor)
- Patient is not achieving complete inhibition at the maximum assigned dose
- Planned or actual pregnancy or breast feeding (females).

If a patient is withdrawn, a decision to recruit an additional patient will be made by the Investigator and Sponsor. Screen failures can be considered for re-screening at the discretion of the Medical Director.

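### Section 12.6 declares an ITT primary analysis, then limits efficacy data to on-protocol measurements, so LDH values from periods of missed doses can drop out

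*Combined protocol and SAP*

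**What the plan says.** **Analysis rules.** Section 12.6 makes five relevant statements:

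- The primary analysis is ITT and covers everyone who consents.
- A per-protocol analysis is added if that set differs from the dosed patients. Missed doses are the example given of a major violation.
- Efficacy at each time point is analysed in every patient who gets to it.
- Safety analysis covers all patients, whether or not they complete as planned.
- The final sentence says the efficacy analysis takes in the measurements obtained while the patient was adhering correctly to the protocol.

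Section 12.1 sets the methods. With fewer than 4 patients, each is analysed separately by linear regression on the full set of measurements, and no formal SAP is written. With 4 or more, a paired t-test compares baseline with the mean of Days 43, 60, 90, 120, 150 and 180, and a mixed model on the full set of measurements is added. Section 12.3 makes all tests descriptive. Section 12.4 leaves irretrievable missing data out of the analysis.

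**Non-adherence.** Section 6.1 covers a patient on 45 mg once daily with an inadequate response: "If compliance is not considered satisfactory the patient should be retrained and re-ablated (60 mg followed by 30 mg 12 hours later) then continue", with the once-daily dose unchanged. The patient is rechecked after 1-2 weeks: "If no improvement is seen the patient should be switched to 22.5 mg q.12h". Patients whose response is still inadequate 3 weeks after that switch "will be deemed treatment failures and withdrawn from the study". Section 6.3 opens its list with "A patient may be withdrawn in any of the following circumstances" and includes "Patient is non-compliant with study procedures in the opinion of the Investigator (mandatory withdrawal" as one entry.

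**The concern.** The trial relies on self-injection at home through Day 180, and Section 5.4 is devoted to missed doses. Section 6.1 keeps some non-adherent patients on drug and in follow-up. LDH measured during non-adherence is therefore expected data, and an ITT analysis exists to retain it.

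The last sentence of Section 12.6 points the other way. If it governs the primary analysis, the values most likely to be removed are those taken when dosing had lapsed. Where control is poor in that period, the on-treatment mean falls and the reported LDH reduction rises, although the patient did no better. The primary analysis would then carry the ITT label on what is in effect an on-protocol data set. At stake is the size of the reported LDH effect in a trial of at most 6 patients, where one patient's values carry visible weight.

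**Working it through.** The plan gives no effect size, SD or power figure (Section 12.2 states only the maximum of 6), so there is no stated result to reproduce. The check is textual, followed by an illustration of size.

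**Step 1: the sentences of Section 12.6 against each other.**

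- The ITT sentence fixes who is in the primary analysis, with no adherence condition.
- The time-point sentence fixes whose data are used at each visit, again with no adherence condition.
- The per-protocol provision already gives missed doses their own analysis.
- The closing sentence adds an adherence condition on measurements and is not limited to the per-protocol analysis.

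Under the first two, a Day 90 LDH taken after a week of missed doses is in. Under the last, it is out. Section 12.1 adds to the conflict: its regression and its mixed model are both specified on every measurement.

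**Step 2: size, by assumption.** Suppose a patient has m LDH values among the six endpoint days, and one of them lies d above the others, which share a level L. Assume the visit mean is taken over the available values.

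- Mean with all values: L + d/m.
- Mean after dropping that value: L.
- Shift: d/m, which inflates the patient's reported reduction by the same amount.

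Take d = 0.8 x ULN. This borrows the size of the single-reading LDH trigger in Section 6.1; it is not an estimate.

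| Values collected (m) | Patient shift, 0.8/m | Group of 6 | Group of 4 |
|---|---|---|---|
| 6 | 0.8/6 = 0.13 x ULN | 0.133/6 = 0.02 x ULN | 0.133/4 = 0.03 x ULN |
| 2 | 0.8/2 = 0.40 x ULN | 0.40/6 = 0.07 x ULN | 0.40/4 = 0.10 x ULN |

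The group columns assume one affected patient. The shift scales in proportion to d.

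**Step 3: where these figures apply.** They describe the paired comparison used with 4 or more patients. With fewer than 4, Section 12.1 fits a regression to each patient; the effect of removing a point then depends on its day and on the rest of the series, so the table gives no figure for that case.

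**Step 4: early termination.** Table 11 collects this visit in the Day 180 column. Neither Section 12.1 nor 12.6 says how an LDH taken there on some other day enters the analysis. The endpoint in Section 3.2 is a mean over six named days, so adding the value to that mean would redefine the endpoint. The mixed model and the regression can take it at its actual day.

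**Step 5: Section 6.3 beside Section 6.1.** The two overlap for one kind of patient: on 45 mg once daily, with an inadequate response and poor dosing compliance. The Section 6.1 route takes 7-14 days to recheck plus 21 days on 12-hourly dosing, or 28-35 days. Any three consecutive endpoint visits span at least 90 - 43 = 47 days (41 with the ±3-day windows). Immediate withdrawal therefore costs at most two endpoint visits if control would not have been regained. If retraining would have worked, it costs all the remaining visits, up to six.

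**The case against.** **On Section 12.6.** The closing sentence does not contain the word only, and ITT could be read as defining the patients while that sentence describes the measurements. Neither point rescues the text. If the sentence does not restrict data it has no function, and an ITT set stripped of off-adherence values no longer does what ITT is for. With 4 or more patients a SAP could resolve the matter; with fewer than 4, Section 12.1 says none will be written.

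**On size.** The illustrated group shift is small. Against baseline LDH at the entry floor of 1.5 x ULN (Section 4.1), 0.022/1.5 = 1.5% and 0.10/1.5 = 6.7%, and less for a higher baseline. Tests are descriptive, so no pass/fail result turns on it. This stands, and it limits the importance of the point.

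**On Section 6.3.** A reader might infer that it compels withdrawal of any non-compliant patient and so contradicts Section 6.1. The documents do not support that:

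- The list is introduced permissively ("A patient may be withdrawn in any of the following circumstances") and the trigger is the Investigator's own opinion.
- Section 6.1 is the specific rule for dosing non-compliance with inadequate response.
- Section 6.1 puts reversion to 12-hourly dosing in consultation with the Sponsor's Medical Director. Section 6.2 asks for discussion with the Medical Directors before either reversion or withdrawal.
- Study procedures may not include dosing at all, since the opening of Section 6.3 names the two separately: "the patient will not undergo any further study-specific procedures or receive any treatment mandated by the Protocol". Table 11 lists drug administration among its procedures, so this reading is open but not secure.
- Section 5.3 offers "or consideration should be given to the patient withdrawing from the study" as an option, and its table directs withdrawal only for inadequate response on 22.5 mg 12-hourly.

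What remains is a missing cross-reference.

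**Conclusion.** The inconsistency in Section 12.6 is real and worth correcting. As written, LDH values from periods of missed doses can be excluded from an analysis labelled ITT, and the reported reduction is overstated if control is poor in those periods. The true size cannot be derived from the documents. Under the stated assumption (one value, 0.8 x ULN above the rest, one affected patient), the shift is 0.13-0.40 x ULN for that patient's mean and 0.02-0.10 x ULN for a group of 4 to 6. If LDH is no worse during non-adherence, there is no bias. The consequence is for the reported estimate only.

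Two further inferences go too far. The patient-level shift does not carry over undiluted to a trial of fewer than 4 patients, because the analysis there is a regression. Nor should failure of the Section 6.1 steps become a precondition for all withdrawals for non-compliance. Those steps cover only patients on 45 mg once daily with inadequate response, and they end on response rather than compliance, so other persistently non-compliant patients could never meet the condition. The precondition would not bind in any case, since "If discontinuation is considered necessary by the Investigator and/or Sponsor (mandatory withdrawal" is a separate entry that carries the same tag.

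**What to change.** In Section 12.6:

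- State that the primary ITT efficacy analysis includes all observed scheduled LDH values regardless of dosing adherence.
- Confine the adherence restriction in the closing sentence to the per-protocol analysis.
- State that an early-termination LDH is used at its actual day in the mixed model (4 or more patients) or the regression (fewer than 4), leaving the six-day mean in Section 3.2 unchanged.

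This needs no new visits, samples or analyses; the early-termination visit, the mixed model, the regression and the per-protocol analysis are already planned. It is a text amendment, subject to the review that Section 14.2 requires for amendments. The downside for the sponsor is a possibly smaller reported LDH reduction.

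Optional and minor, in Section 6.3: add that for a patient on 45 mg once daily with inadequate response and unsatisfactory dosing compliance, the Section 6.1 retraining steps and the Medical Director discussion in Sections 6.1 and 6.2 come before withdrawal for non-compliance. Leave the criterion as it is for other non-compliant patients.
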